### **9.2.1. Serious Adverse Events**

An SAE is any AE from this study that results in 1 of the following:

- death
- initial or prolonged inpatient hospitalization
- a life-threatening experience (that is, immediate risk of dying)
- persistent or significant disability/incapacity
- congenital anomaly/birth defect
- important medical events that may not be immediately life-threatening or result in death or hospitalization but may jeopardize the patient or may require intervention to prevent 1 of the other outcomes listed in the definition above
- when a condition related to the injection syringe or IV drug delivery system necessitates medical or surgical intervention to preclude either permanent impairment of a body function or permanent damage to a body structure, the serious outcome of "required intervention" will be assigned.

Study site personnel must alert the Lilly CRP/clinical pharmacologist, or its designee, of any SAE as soon as practically possible.

Additionally, study site personnel must alert Lilly Global Patient Safety, or its designee, of any SAE within 24 hours of investigator awareness of the event via a sponsor-approved method. If alerts are issued via telephone, they are to be immediately followed with official notification on study-specific SAE forms. This 24-hour notification requirement refers to the initial SAE information and all follow-up SAE information.

Although all AEs are recorded in the electronic data entry/designated data transmission methods after signing informed consent, SAE reporting to the sponsor begins after the patient/subject has signed informed consent and has received IP. However, if an SAE occurs after signing informed consent, but prior to receiving IP, AND is considered Reasonably Possibly Related to a study procedure then it MUST be reported.

Investigators are not obligated to actively seek AEs or SAEs in subjects once they have discontinued from and/or completed the study (the patient/subject summary eCRF has been completed). However, if the investigator learns of any SAE, including a death, at any time after a subject has been discharged from the study, and he/she considers the event reasonably possibly related to the study treatment or study participation, the investigator must promptly notify Lilly.

Pregnancy (maternal or paternal exposure to IP) does not meet the definition of an AE. However, to fulfill regulatory requirements any pregnancy should be reported following the SAE process to collect data on the outcome for both mother and fetus.

### **9.2.1.1. Suspected Unexpected Serious Adverse Reactions**

Suspected unexpected serious adverse reactions (SUSARs) are serious events that are not listed in the IB and that the investigator reports as related to IP or procedure. Lilly has procedures that will be followed for the recording and expedited reporting of SUSARs that are consistent with global regulations and the associated detailed guidances.

### **9.2.2. Complaint Handling**

Lilly collects product complaints on IPs and drug delivery systems used in clinical trials in order to ensure the safety of study participants, monitor quality, and to facilitate process and product improvements.

Patients/subjects should be instructed to contact the investigator as soon as possible if he or she has a complaint or problem with the IP so that the situation can be assessed.

## **9.3. Treatment of Overdose**

For the purposes of this study, an overdose of LY3316531 is considered any dose higher than the dose assigned through randomization. There is no specific antidote to LY3316531 and in the case of overdose, subjects should be observed and treated with the appropriate supportive care.

Refer to the IB for LY3316531.

## **9.4. Safety**

### **9.4.1. Laboratory Tests**

For each patient/subject, laboratory tests detailed in [Appendix 2](#) should be conducted according to the Schedule of Activities (Section 2).

With the exception of safety laboratory test results that may unblind the study, Lilly or its designee will provide the investigator with the results of laboratory tests analyzed by a central vendor, if a central vendor is used for the study.

### **9.4.2. Vital Signs**

For each patient/subject, vital sign measurements should be conducted according to the Schedule of Activities (Section 2) and as clinically indicated. Vital sign measurements may be repeated at the discretion of the investigator.

Blood pressure and pulse rate should be measured after at least 5 minutes supine (or semi-recumbent if subject is unable to lie supine).

If orthostatic measurements are required, patients/subjects should be supine for at least 5 minutes and stand for at least 3 minutes.

If the patient/subject feels unable to stand, supine vital signs only will be recorded.

Unscheduled orthostatic vital signs should be assessed, if possible, during any AE of dizziness or posture-induced symptoms. Additional vital signs may be measured during each study period if warranted.

Body temperature will be measured as specified in the Schedule of Activities (Section 2) and as clinically indicated.

Body weight will be recorded as specified in the Schedule of Activities (Section 2) and as clinically indicated.

#### **9.4.3. *Electrocardiograms***

For each subject in Part A, a centralized 12-lead digital ECG will be collected as triplicates according to the Schedule of Activities (Section 2), except at screening where a single ECG will be collected.

For each patient/subject in Parts B and C, a single ECG will be collected locally and stored at the investigator's site unless the ECG values for subjects in Part A show clinically significant changes (for example, increase in PR or QT interval). In this situation, the ECGs for patients/subjects in Parts B and/or C will be collected as in Part A of the study.

Electrocardiograms should be recorded up to 5 minutes before collecting any blood for safety or PK tests. Consecutive triplicate ECGs will be obtained at approximately 1-minute intervals. Patients/subjects should be supine for approximately 5 minutes before ECG collection and remain supine, but awake, during ECG collection. Electrocardiograms may be obtained at additional times, when deemed clinically necessary. Collection of additional ECGs at a particular time point is allowed to ensure high-quality records.

Electrocardiograms will be interpreted by a qualified physician (the investigator or qualified designee) at the site as soon after the time of ECG collection as possible, and ideally while the subject is still present, to determine whether the patient/subject meets entry criteria at the relevant visit(s) and for immediate patient/subject management should any clinically relevant findings be identified.

If a clinically significant quantitative or qualitative change from baseline is identified after enrollment, the investigator will assess the patient/subject for symptoms (for example, palpitations, near syncope, syncope) to determine whether the patient/subject can continue in the study. The investigator or qualified designee is responsible for determining if any change in patient/subject management is needed and must document his/her review of the ECG printed at the time of evaluation from at least 1 of the triplicate ECGs from each time point.

Digital ECGs will be electronically transmitted to a central ECG laboratory designated by Lilly. The central ECG laboratory will perform a basic quality control check (for example, demographics and study details) then store the ECGs in a database. At a future time, the stored ECG data may be overread at the central ECG laboratory for further evaluation of machine-read measurements or to meet regulatory requirements.

The machine-read ECG intervals and heart rate may be used for data analysis and report writing purposes unless a cardiologist overread of the ECGs is conducted prior to completion of the final study report (in which case the overread data would be used).

#### **9.4.4. Safety Monitoring**

The Lilly clinical pharmacologist or CRP/scientist will monitor safety data throughout the course of the study.

Lilly will review SAEs within time frames mandated by company procedures. The Lilly clinical pharmacologist or CRP will periodically review the following data:

- trends in safety data
- laboratory analytes
- adverse events including monitoring of incidence and nature of any infections, infusion reactions, and injection-site reactions.

When appropriate, the Lilly clinical pharmacologist or CRP will consult with the functionally independent Global Patient Safety therapeutic area physician or clinical research scientist.

##### **9.4.4.1. Hepatic Safety**

If a study patient/subject experiences elevated ALT  $\geq 3 \times$  ULN, ALP  $\geq 2 \times$  ULN, or elevated TBL  $\geq 2 \times$  ULN, liver tests ([Appendix 4](#)) should be repeated within 3 to 5 days including ALT, AST, ALP, TBL, direct bilirubin, gamma-glutamyl transferase, and creatinine kinase to confirm the abnormality and to determine if it is increasing or decreasing. If the abnormality persists or worsens, clinical and laboratory monitoring should be initiated by the investigator based on consultation with the Lilly clinical pharmacologist or CRP. Monitoring should continue until levels normalize and/or are returning to approximate baseline levels.

Additional safety data should be collected if 1 or more of the following conditions occur:

- elevation of serum ALT to  $\geq 5 \times$  ULN on 2 or more consecutive blood tests
- elevation of serum TBL to  $\geq 2 \times$  ULN (except for cases of known Gilbert's syndrome)
- elevation of serum ALP to  $\geq 2 \times$  ULN on 2 or more consecutive blood tests
- patient/subject discontinued from treatment due to a hepatic event or abnormality of liver tests
- hepatic event considered to be an SAE.

#### 9.4.4.3. C-SSRS

The Columbia-Suicide Severity Rating Scale (C-SSRS) captures the occurrence, severity, and frequency of suicidal ideation and/or behavior during the assessment period (Posner et al. 2011; Columbia University Medical Center [WWW]). The scale includes suggested questions to solicit the type of information needed to determine if suicidal ideation and/or behavior occurred. The C-SSRS is administered by an appropriately trained health care professional with at least 1 year of patient care/clinical experience. The tool was developed by the National Institute of Mental Health trial group for the purpose of being a counterpart to the Columbia Classification Algorithm of Suicide Assessment categorization of suicidal events.

The nonleading AE collection should occur prior to the collection of the C-SSRS. If a suicide-related event is discovered *during the C-SSRS* but was not captured during the nonleading AE collection, sites should not change the AE form. If an event is serious or leads to discontinuation, this is an exception where the SAE and/or AE leading to discontinuation should be included on the AE form and the process for reporting SAEs should be followed.

### 9.5. Pharmacokinetics

At the visits and times specified in the Schedule of Activities (Section 2), venous blood samples of approximately 5 mL each will be collected to determine the serum concentrations of LY3316531. A maximum of 2 samples may be collected at additional time points during the study if warranted and agreed upon between both the investigator and sponsor. Instructions for the collection and handling of blood samples will be provided by the sponsor. The actual date and time (24-hour clock time) of each sampling will be recorded.

Drug concentration information that may unblind the study will not be reported to investigative sites or blinded personnel until the study has been unblinded.

### **9.5.1. Bioanalysis**

Samples will be analyzed at a laboratory approved by the sponsor and stored at a facility designated by the sponsor.

Serum concentrations of LY3316531 will be assayed using validated enzyme-linked immunosorbent assay methods. Analyses of samples collected from subjects who received placebo are not planned.

Bioanalytical samples collected to measure study drug concentrations will be retained for a maximum of 1 year following last subject visit for the study. During this time, samples remaining after the bioanalyses may be used for exploratory metabolism studies or exploratory analyses such as bioanalytical assay validation or cross-validation exercises.

## **9.6. Pharmacodynamics**

Measurements of total CGRP concentrations will be used to evaluate target engagement in Part A of the study. Samples collected in Parts B and C of the study will be analyzed based on the concentrations of total CGRP observed in Part A. Samples for CGRP measurements will be analyzed in a validated assay at a laboratory approved by the sponsor and stored at a facility designated by the sponsor.

The sample(s) will be stored for up to a maximum of 15 years after the last patient/subject visit for the study at a facility selected by the sponsor.

### **9.6.1. Pharmacodynamic Assessments**

The image consists of three large, bold, red letters 'C', 'C', and 'I' arranged vertically. They are set against a solid black rectangular background.

#### **9.6.1.2. Disease Activity Measures for Patients with Psoriasis**

The disease activity measures described below will be collected at the times shown in the Schedule of Activities (Section 2.3).

- The PASI scores the severity of disease on a scale from 0 to 72 (where a score of 72 indicates extreme disease severity) by combining assessments of the extent of body surface involvement in the head, trunk, arms, and legs together with the severity of desquamation, erythema, and plaque induration.
- Percent BSA will be evaluated as the percent involvement of psoriasis on each patient's BSA on a continuous scale from 0% (no involvement) to 100% (full involvement), where 1% corresponds to the size of the patient's hand (including the palm, fingers, and thumb) (National Psoriasis Foundation 2009).
- The sPGA provides the physician's determination of the patient's psoriasis lesions overall at a given time point. Overall lesions are graded for induration, erythema, and

scaling, and the sum of the 3 scores is divided by 3 to obtain a final sPGA score (range 0 to 5). For the analysis of responder rates, the sPGA scores are rounded to the nearest whole number, and the patient's psoriasis is assessed as clear (0), minimal (1), mild (2), moderate (3), severe (4), or very severe (5).

- In the Patient's Global Assessment of Disease Severity, patients are asked to rank on a 0 to 5 numeric rating scale the severity of their psoriasis "today" from 0 (clear; no psoriasis) to 5 (severe; worst their psoriasis has ever been).
- The Psoriasis Symptom Scale (PSS) is a patient-reported assessment of 8 symptoms: itch, pain, discomfort, stinging, burning, redness, scaling, and cracking. Respondents are asked to answer the questions based on their psoriasis symptoms. Numeric rating scales are used to assess the self-reported overall severity of each of the 8 symptoms individually on an 11-point horizontal scale anchored at 0 (no) and 10 (worst imaginable). The overall severity for each individual symptom from psoriasis is indicated by selecting the number from 0 to 10 that best describes the worst level of each symptom in the preceding 24 hours. The instructions for completion are embedded within the PSS questionnaire for subjects to read before responding to the items. The symptom severity scores, ranging from 0 to 10, are the values of the selected numbers indicated by the subject on the instrument's horizontal scale. Each of the 8 individual items will receive a score of 0 to 10 and will be reported as item scores for itch, pain, discomfort, stinging, burning, redness, scaling, and cracking. In addition, a total score ranging from 0 (no psoriasis symptoms) to 80 (worst imaginable psoriasis symptoms) will be reported.

### ***9.6.2. Immunogenicity Assessments***

At the visits and times specified in the Schedule of Activities (Section 2), venous blood samples will be collected to determine antibody production against the LY3316531. To interpret the results of immunogenicity, a PK sample will be collected at the same time points. All samples for immunogenicity should be taken predose when applicable. In the event of drug hypersensitivity reactions (immediate or non-immediate), additional samples will be collected as close to the onset of the event as possible, at the resolution of the event, and 30 days following the event. Instructions for the collection and handling of blood samples will be provided by the sponsor. The actual date and time (24-hour clock time) of each sampling will be recorded.

Immunogenicity will be assessed by a validated assay designed to detect ADAs in the presence of LY3316531 at a laboratory approved by the sponsor. Antibodies may be further characterized and/or evaluated for their ability to neutralize the activity of LY3316531. Patients/subjects who are treatment-emergent (TE) ADA positive at the end of the study or early discontinuation will be followed up with samples taken approximately every 3 months, until they return to 2-fold titer of baseline or for a maximum of 1 year. Treatment-emergent ADAs are defined in Section 10.3.4.

Samples will be retained for a maximum of 15 years after the last patient/subject visit, or for a shorter period if local regulations and ERBs allow, at a facility selected by the sponsor. The

duration allows the sponsor to respond to future regulatory requests related to LY3316531. Any samples remaining after 15 years will be destroyed.

## 9.7. Genetics

A blood sample will be collected for pharmacogenetic analysis as specified in the Schedule of Activities (Section 2), where local regulations allow.

Samples will not be used to conduct unspecified disease or population genetic research either now or in the future. Samples will be used to investigate variable exposure or response to LY3316531 and to investigate genetic variants thought to play a role in psoriasis. Assessment of variable response may include evaluation of AEs or differences in efficacy.

All samples will be coded with the patient/subject number. These samples and any data generated can be linked back to the patient/subject only by the investigative site personnel.

Samples will be retained for a maximum of 15 years after the last patient visit, or for a shorter period if local regulations and/or ERBs impose shorter time limits, for the study at a facility selected by Lilly or its designee. This retention period enables use of new technologies, response to regulatory questions, and investigation of variable response that may not be observed until later in the development of LY3316531 or after LY3316531 is commercially available.

Molecular technologies are expected to improve during the 15-year storage period and therefore cannot be specifically named. However, existing approaches include whole genome or exome sequencing, genome-wide association studies, multiplex assays, and candidate gene studies. Regardless of technology utilized, data generated will be used only for the specific research scope described in this section.

CCI

## **9.9. Health Economics**

This section is not applicable for this study.

## 10. Statistical Considerations and Data Analysis

### 10.1. Sample Size Determination

The sample size for each cohort is customary for the first-in-human study in which formal power analyses is not necessary to address the objectives associated with safety, tolerability, PK, and/or PD assessments. Approximately 86 patients/subjects are planned for enrollment; however, up to 102 subjects may be enrolled to allow for replacement of subjects and any additional dose cohorts (Parts A, B, and C).

Subjects/patients who withdraw from the study before completing the Day 57 (Part A) or Day 85 (Parts B and C) assessment may be replaced if necessary to have the planned number of subjects/patients complete a dose cohort. A replacement subject/patient will be assigned the same treatment as the subject/patient he or she replaces (Parts A, B, and C).

### 10.2. Populations for Analyses

#### 10.2.1. Study Participant Disposition

A detailed description of patient/subject disposition will be provided at the end of the study.

All subjects who discontinue from the study will be identified, and the extent of their participation in the study will be reported. If known, a reason for their discontinuation will be given. A disposition table for all enrolled subjects will be provided.

#### 10.2.2. Study Participant Characteristics

The subject's/patient's age, sex, weight, height, racial designation, or other demographic and study disease characteristics will be recorded and summarized.

### 10.3. Statistical Analyses

Statistical analysis of this study will be the responsibility of Eli Lilly and Company or its designee.

Pharmacokinetic/PD analyses (CGRP target engagement) will be conducted on data from all patients/subjects who receive at least 1 dose of the IP and have evaluable PK.

Clinical activity and PD analyses will be conducted for all patients with psoriasis who receive the study drug (Part C only).

Safety analyses will be conducted for all enrolled patients/subjects, whether or not they completed all protocol requirements.

All protocol deviations that occur during the study will be considered for their severity/impact and will be taken into consideration when subjects are assigned to analysis populations prior to database lock and unblinding. Details of subject assignment to the analysis populations will be listed.

The placebo data from all cohorts will be pooled across all dose-escalation cohorts for the purpose of analysis.

Additional exploratory analyses of the data will be conducted as deemed appropriate. Study results may be pooled with the results of other studies for population PK analysis purposes to avoid issues with post hoc analyses and incomplete disclosures of analyses.

### **10.3.1. Safety Analyses**

#### **10.3.1.1. Clinical Evaluation of Safety**

All IPs and protocol procedure AEs will be listed, and if the frequency of events allows, safety data will be summarized using descriptive methodology.

The incidence of symptoms for each treatment will be presented by severity and by association with IP as perceived by the investigator. Symptoms reported to occur prior to treatment with study drug will be distinguished from those reported as new or increased in severity during the study. Each symptom will be classified by the most suitable term from the Medical Dictionary for Regulatory Activities.

Safety analyses will include summaries of the following:

- AEs and SAEs, including severity and possible relationship to study drug
- laboratory measures

CCI

The number of IP-related SAEs will be reported and summarized by preferred term.

Suicidal ideation and/or behavior and self-injurious behavior with no suicidal intent, based on the C-SSRS, will be listed by patient/subject (Parts B and C).

#### **10.3.1.2. Statistical Evaluation of Safety**

Safety parameters that will be assessed include safety laboratory parameters, vital signs, and ECG parameters. The parameters will be listed, and summarized using standard descriptive statistics. Additional analysis will be performed if warranted upon review of the data.

Baseline for safety parameters will be defined as the last evaluable value before the first dose.

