9. STATISTICAL METHODOLOGY

9.1 General

Data listings will be provided for all data in the database. Summary statistics and statistical analysis will only be presented for data where detailed in this SAP. For continuous data, summary statistics will include the arithmetic mean, arithmetic standard deviation (SD), median, minimum, maximum, and number of data points (N). For log-normal data, the geometric mean and geometric coefficient of variation (CV%) will also be presented. For categorical data, frequency counts and percentages will be presented. Data listings will be provided for all subjects up to the point of withdrawal, with any subjects excluded from the relevant population highlighted. Summary statistics and statistical analyses will generally only be performed for subjects included in the relevant analysis population. For the calculation of summary statistics and statistical analysis, unrounded data will be used.

Mean change from baseline is the mean of all individual subjects' change from baseline values. Each individual change from baseline will be calculated by subtracting the individual subject's baseline value from the value at the timepoint. The individual subject's change from baseline values will be used to calculate the mean change from baseline using a SAS procedure such as Proc Univariate.

Data analysis will be performed using SAS® Version 9.4 or greater.

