9.5.3 Clinical laboratory parameters

All clinical chemistry and hematology data will be summarized by parameter and treatment, and listed. Urinalysis data will be listed. Additionally clinical chemistry, hematology and urinalysis data outside the reference ranges will be listed.

Values for any clinical chemistry, hematology and urinalysis values outside the reference ranges will be flagged on the individual subject data listings.

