9.5.4 Vital signs

Vital signs data will be summarized by treatment together with changes from baseline, where baseline is defined as Day 1 predose. Figures of mean vital signs and mean changes from baseline profiles by treatment will be presented by treatment.

Furthermore, values for individual subjects will be listed.

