9.5.5 Electrocardiogram (ECG)

The ECG data will be obtained directly from the 12-lead ECG traces. These data include the PR, QT, QTcB intervals, QRS duration and heart rate, where QTcB is the QT interval corrected using Bazett's formula. In addition, QTcF (the QT interval corrected using Fridericia's formula) will be calculated as follows:

$$QTcF = \frac{QT}{\sqrt[3]{(60/HR)}}$$

The ECG data will be summarized by treatment together with changes from baseline, where baseline is defined as Day 1 predose. Figures of mean ECG data and mean changes from baseline will be presented by treatment. The frequency of subjects with a maximum increase from baseline in QTcB and QTcF interval will be summarized for each treatment according to the following categories: >30 ms and >60 ms. In addition, the frequency of subjects with QTcB and QTcF postdose values, according to the following categories: >450 ms, >480 ms and >500 ms, will be summarized by treatment.

A plasma LY3316531 concentration-QT analysis will be performed to assess the changes from baseline (Day 1 predose) QTcF interval relative to plasma LY3316531 concentrations across all active treatments. The change from baseline adjustment will be based on individual subject's Day 1 predose value. The analysis will be performed by plotting change from baseline QTcF against LY3316531 concentrations, including all post Day 1 dosing timepoints. The plot will be produced separately for parts A, B, and C of the study. Each plot will include a simple linear regression.

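### SAP 9.5.3 plans no change-from-baseline or shift summary for chemistry and hematology, although the protocol defines a baseline for safety laboratory parameters and the SAP uses change from baseline for vital signs, ECG and HS-CRP

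*Protocol*

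**What the plan says.** Protocol 10.3.1.2 treats the three kinds of safety measurement together: "Safety parameters that will be assessed include safety laboratory parameters, vital signs, and ECG parameters". They are to be listed and summarised descriptively, with further analysis if the data call for it. One baseline is given for all of them: "Baseline for safety parameters will be defined as the last evaluable value before the first dose".

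The SAP then treats them differently:

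- Vital signs (SAP 9.5.4): "Vital signs data will be summarized by treatment together with changes from baseline, where baseline is defined as Day 1 predose".
- ECG (SAP 9.5.5): "The ECG data will be summarized by treatment together with changes from baseline, where baseline is defined as Day 1 predose", with counts of QTc increases as well.
- HS-CRP (SAP 9.4.1.5): values and change from baseline.
- Chemistry and hematology (SAP 9.5.3): "All clinical chemistry and hematology data will be summarized by parameter and treatment, and listed". The section goes on: "Additionally clinical chemistry, hematology and urinalysis data outside the reference ranges will be listed". Out-of-range values are also flagged in the individual listings. No baseline, change, shift table or time point is mentioned.

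SAP 9.1 explains how a mean change from baseline is calculated, but also sets a limit: "Summary statistics and statistical analysis will only be presented for data where detailed in this SAP". SAP 11 reports no changes from the protocol's analyses.

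**The concern.** Safety is the primary objective, and routine chemistry and hematology are the safety measurements for which the SAP text never uses the protocol's baseline. Because SAP 9.1 restricts summaries to those the SAP details, its general formula for mean change does not supply one for laboratory data.

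The out-of-range listing does not fully stand in for a change analysis, for two reasons:

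- Participants may enter with abnormal values. Inclusion criterion [4] admits healthy subjects with deviations judged not clinically significant. Criterion [12] admits patients with ALT, AST and creatinine up to 2 times ULN. The listing rule does not separate values already abnormal before dosing from those that became abnormal or worsened afterwards. SAP 9.5.1 does make that separation for adverse events.
- A drug effect that moves most participants in one direction but keeps them inside the reference range triggers no flag.

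Active groups have 3 to 8 participants. At that size a difference in raw postdose means may reflect who was enrolled as much as what the drug did. In Part C there is no placebo group, so within-patient change is the only contrast available inside that part.

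**Working it through.** **Group sizes.** From Protocol Table FFAA.5.1 and SAP Table 1:

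- Part A: active 3 + 3 + 6 + 6 + 6 + 6 + 6 = 36; placebo 1 + 1 + 2 + 2 + 0 + 2 + 2 = 10; total 46.
- Part B: active 12, placebo 4; total 16.
- Part C: active up to 24, no placebo.
- Planned total: 46 + 16 + 24 = 86. Maximum: 52 + 20 + 30 = 102. Both match Protocol 10.1 and SAP 7.

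SAP 6 pools placebo within each part, so each Part A active group of 3 or 6 is set against 10 placebo subjects.

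**Chance difference at baseline.** With between-subject SD σ, the SD of the difference between two group means before any dosing is σ√(1/n_active + 1/n_placebo):

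- 3 against 10: √(1/3 + 1/10) = 0.658σ.
- 6 against 10: √(1/6 + 1/10) = 0.516σ.
- Part B, 6 against 4: √(1/6 + 1/4) = 0.645σ.

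**Raw values against change from baseline.** Let ρ be the correlation between a subject's pre- and postdose values, with equal variance at both times. The SD of change is σ√(2(1 − ρ)), so the SE of the active-placebo difference is multiplied by √(2(1 − ρ)). The documents give no value for ρ, so a range is shown.

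| ρ (assumed) | √(2(1 − ρ)) | SE, 3 vs 10 | SE, 6 vs 10 | Against raw values |
|---|---|---|---|---|
| raw values | 1 | 0.658σ | 0.516σ | – |
| 0.3 | 1.183 | 0.779σ | 0.611σ | 18% larger |
| 0.5 | 1.000 | 0.658σ | 0.516σ | no gain |
| 0.7 | 0.775 | 0.510σ | 0.400σ | 22% smaller |
| 0.8 | 0.632 | 0.416σ | 0.327σ | 37% smaller |

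Change from baseline always subtracts the observed baseline difference. It improves precision only when ρ is above 0.5.

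**Part C.** With 8 patients, the SE of the mean change is σ√(2(1 − ρ))/√8: 0.274σ at ρ = 0.7 and 0.224σ at ρ = 0.8. Suppose the table gave means by visit and a reader subtracted them. The mean change would be recovered if data were complete, but not its spread. Treating the two means as independent (ρ = 0) would give √2/√8 = 0.500σ, about twice the value that applies under those correlations.

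**Which baseline fits.** The Schedules of Activities (Protocol 2.1 to 2.3) place predose chemistry and hematology at screening and Day -1. The definition in SAP 9.5.4 and 9.5.5, Day 1 predose, would find no scheduled laboratory sample. The protocol's last evaluable value before the first dose does.

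**The case against.** The other side has real force on several points:

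- **No breach of the protocol.** A reader might infer that the SAP contradicts the protocol. It does not. Protocol 10.3.1.2 asks only for listings and standard descriptive statistics, and defining a baseline is not a promise of a change table. This is an omission.
- **The tables have not been seen.** SAP 3 puts the detailed table descriptions in a separate shell document, which may already contain change columns. It therefore cannot be said that no laboratory change will be reported, only that the SAP text does not call for it.
- **Effects are not hidden outright.** A reader might infer that a laboratory effect would vanish among between-subject differences. All data are listed and out-of-range values flagged, and with 3 to 8 people per active group each person's course can be read. An abnormal Day -1 value would be flagged alongside later values. If the summary has visit rows, mean change follows by subtraction when data are complete.
- **Escalation is not affected.** A reader might infer that dose decisions suffer. Protocol 7.4.2 and 10.3.5 base them on ongoing review of individual safety data, not on these end-of-study tables.
- **The primary endpoint already covers some of this.** It is the incidence of adverse events. An abnormal laboratory finding can be one (Protocol Appendix 1), and treatment-emergent events include worsening from the pretreatment state.
- **The precision gain is conditional.** It depends on an unstated correlation and reverses below 0.5. SAP 9.5.15 also plans no inferential safety analysis.

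All of this narrows the point but does not remove it. Listings do not summarise a common drift within range. Subtracting means gives neither the spread of individual change nor shift counts, and fails when participants drop out. Further analysis if warranted begins only after someone has noticed a signal.

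**Conclusion.** The gap is real and modest. SAP 9.5.3 leaves out, for chemistry and hematology, the change from baseline that the SAP gives to vital signs, ECG and HS-CRP, although the protocol's baseline covers all safety parameters. The losses are the summary of consistent within-range drift, the spread of individual change, and a clear separation of new or worsened abnormalities from those allowed at entry.

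It matters most in Part A, where a chance baseline difference has an SD of 0.66 or 0.52 between-subject SD, and in Part C, which has no control. A 22% to 37% reduction in SE rests on an assumed correlation of 0.7 to 0.8 and equal variances. At 0.5 there is no gain, and at 0.3 the SE is 18% larger. The case for change does not rest on precision alone, since it also takes out the observed baseline difference and describes what happened within each person.

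The documents do not support saying that laboratory effects would go unseen, that escalation is compromised or that the SAP departs from the protocol. This is an inexpensive improvement that should be made.

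**What to change.** Amend SAP 9.5.3 as follows:

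1. Summarise chemistry and hematology by treatment and time point, both as values and as change from baseline. Define baseline as the last evaluable value before the first dose, as in Protocol 10.3.1.2, and not as Day 1 predose.
2. Add a table of shifts from baseline to the worst postdose category. Use low, normal and high in general. For liver tests and creatinine use categories in multiples of ULN, fixed in advance, because a low/normal/high table cannot show worsening from a baseline that is already high.
3. Flag a postdose out-of-range value as treatment-emergent only if the baseline value was in range or the postdose value is worse than baseline.
4. Confirm that the table shells match. If they already hold change columns, item 1 only brings the SAP text into line.

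The cost is SAP wording and a few extra standard tables. The Day -1 samples are already scheduled in all three parts, so no new samples are needed.
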